### 5.2.1 Primary Analyses of Primary Efficacy Variables

The primary efficacy variable is the change from study baseline post treatment 1 in the daily average frequency of daytime urinary incontinence episodes (daytime is defined as the time between waking up to start the day and going to bed to sleep for the night).

Each daytime period recorded in the bladder diary will be normalized to represent a 12-hour period. The daily average frequency of daytime urinary incontinence episodes will be adjusted by the normalized daytime period.

For BOTOX treatment cycle 1, the treatment difference (least-squares [LS] mean difference) and 95% CI of the treatment difference in mean change from study baseline for 100 versus 25 U of BOTOX and 50 versus 25 U of BOTOX will be calculated. Pairwise comparisons of 100 versus 25 U of BOTOX and 50 versus 25 U of BOTOX up to week 12 posttreatment 1 will be evaluated using an ANCOVA model with study baseline value as covariate, and treatment group as factor. A hierarchical analysis strategy ([Lubsen and Kirwan, 2002](#)) to adjust for multiplicity will be used. In the order of (1) 100 versus 25 U of BOTOX, and (2) 50 versus 25 U of BOTOX, treatment group differences at week 12 will be tested at the 0.05 significance level in a fixed sequence fashion. Results of hypothesis testing for 50 versus 25 U of BOTOX will be considered for statistical significance only if the treatment difference for 100 versus 25 U of BOTOX is shown to be statistically significant. A similar analysis, without a hierarchal testing strategy, will be applied to other timepoints.

For each BOTOX treatment cycle, the mean raw value, mean change from study baseline, and 95% CIs for the arithmetic mean change from the study baseline will be summarized by study visit.

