7.3.1 Primary Efficacy Analyses

The primary efficacy analysis will be based on the BOTOX-treated population, with imputation of missing values as described in Section 7.2.1. The primary timepoint will be week 12 after treatment 1.

For each of the BOTOX doses, descriptive statistics will be provided for the daily average frequency of normalized daytime urinary incontinence episodes at study baseline and week 12, together with the change from study baseline (arithmetic mean); the 95% confidence intervals (CI) of the arithmetic mean change will be provided.

For each of the BOTOX doses of 100 U and 50 U, the null hypothesis is that there is no difference between that dose group and the 25 U BOTOX dose group in mean change from study baseline in daily average frequency of daytime urinary incontinence episodes at week 12. The alternative hypothesis is that there is a difference in mean change from study baseline in daily average frequency of daytime urinary incontinence episodes between that BOTOX dose group and the 25 U dose group at week 12 posttreatment 1.

The hypotheses will be tested using an ANCOVA model with baseline value as covariate and treatment group as a factor.

A hierarchical analysis strategy (Lubsen and Kirwan, 2002) will be used to control type I error due to the multiplicity issues related to the primary efficacy analyses for the primary efficacy variable. In the order of (1) 100 U versus 25 U BOTOX, and (2) 50 U versus 25 U BOTOX, treatment group differences at week 12 posttreatment 1 will be tested at the 0.05 significance level in a fixed sequence fashion. Results of hypothesis testing for 50 U versus 25 U BOTOX will be considered for statistical significance only if the treatment difference for 100 U versus 25 U BOTOX is shown to be statistically significant.

The treatment difference at week 12 posttreatment 1 in mean change from study baseline for 100 U versus 25 U BOTOX and 50 U versus 25 U BOTOX will be calculated, as well as the 95% CI of these differences.

The treatment-by-investigator interaction will be assessed.

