7.3.2.2 Efficacy Analyses for the Secondary Efficacy Variables

The analysis of daytime micturition episodes, daytime urgency episodes, and volume voided per micturition at week 12 after treatment 1 will generally be analyzed as described for the primary efficacy endpoint in Section 7.3.1 except that baseline daytime urinary urgency incontinence episodes (a total of ≤ 6 episodes or > 6 episodes over the 2-day diary collection period) will be included in the ANCOVA model as an additional factor. The hierarchal testing strategy described in Section 7.3.1 will not be implemented.

For the analysis of night time urinary incontinence, the numbers and proportions of patients who experienced night time urinary incontinence on 0, 1, or 2 nights will be presented.

Analysis of time to patient request for retreatment and time to patient qualification for retreatment will be performed as described in Section 7.3.3.9, Duration of Effect.

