### 1.1 Primary Study Objectives and Design

The primary objective is to evaluate the safety and efficacy for the treatment of urinary incontinence due to OAB in patients 12 to 17 years of age who have not been adequately managed with anticholinergic therapy.

Patients may participate in the study for 96 weeks following entry into the study and should have at least 12 weeks follow-up since the last treatment prior to exiting the study. Eligible patients are randomized to 1 of 3 treatment groups in a 1:1:1 ratio:

- 25 units (U) BOTOX (not to exceed 6 U/kg)
- 50 U BOTOX (not to exceed 6 U/kg)
- 100 U BOTOX (not to exceed 6 U/kg)

In order to ensure that an upper dosing limit of 6 U/kg is not exceeded, the actual dose administered will be adjusted based on the patient's weight if necessary.

Patients will be centrally randomized. In order to ensure balance across treatment groups, patients will be stratified by baseline daytime urinary urgency incontinence episodes (a total of  $\leq 6$  episodes or  $> 6$  episodes over the 2-day diary collection period).

Multiple treatments may be administered in this study. Doses received at subsequent retreatments will be determined by the investigator and based on the patient's response to the preceding blinded treatment. The investigator can elect to keep the dose the same or increase the dose compared with the preceding treatment. If it is deemed that a decrease in dose is warranted, the patient will be exited from the study. The first treatment will be administered on day 1.

All patients will be evaluated at scheduled clinic visits at weeks 2, 6, and 12 post-treatment, and thereafter at alternating telephone and clinic visits every 6 weeks until the patient qualifies for further retreatment or exits the study. Patients can request retreatment from week 12 since the preceding treatment. Once qualified for retreatment, the same visit schedule will be followed.

The primary efficacy measure is daytime urinary incontinence episodes, and the primary time point is week 12 after treatment 1.

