### 2.1.1 Handling Mis-stratification

For any analysis that are by stratum or for analysis that adjusts for stratum effect, the actual strata will be used instead of the strata assigned by the site's entry into the IWRS at randomization.

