### **5.3 Secondary Efficacy Analyses**

#### **5.3.1 Proportion of Responders**

Responder analyses will be performed using the daily average frequency of normalized daytime urinary incontinence episodes. The following definitions of responder will be used for daytime urinary incontinence at week 12 post-treatment 1.

1. A responder is a patient who has at least a 50% reduction from study baseline in daily average frequency of normalized daytime urinary incontinence episodes at week 12 post-treatment 1.
2. In addition, the proportions of patients with 100% reduction from study baseline in daily average frequency of normalized daytime urinary incontinence episodes at week 12 post-treatment 1 will be evaluated.

For week 12 posttreatment 1, the difference of the proportions of patients responding between the treatment groups (100 versus 25 U of BOTOX, and 50 versus 25 U of BOTOX) will be analyzed using the Cochran-Mantel-Haenszel (CMH) method controlling for baseline daytime urinary urgency incontinence episodes (a total of  $\leq 6$  episodes or  $> 6$  episodes over the 2-day diary collection period).

For each treatment cycle, the proportion of patients with  $\geq 50\%$ , and 100% reduction from study baseline in normalized daytime urinary incontinence episodes will be presented by treatment group for each post-treatment visit.

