### 5.4.1 Number of Daytime Micturition Episodes

For each treatment cycle, the mean raw value, mean change from study baseline, and 95% CI for the mean change from study baseline in daily average frequency of daytime micturition episodes (arithmetic mean) over the 2-day diary period will be summarized by treatment group at post-treatment visits.

For BOTOX treatment cycle 1, the treatment difference (LS mean difference) and 95% CI of the treatment difference in mean change from study baseline for 100 versus 25 U of BOTOX and 50 versus 25 U of BOTOX will be calculated. Pairwise comparisons of 100 versus 25 U of BOTOX and 50 versus 25 U of BOTOX up to week 12 posttreatment 1 will be evaluated using an ANCOVA model with study baseline value as covariate, and treatment group and stratification (baseline daytime urinary urgency incontinence episodes [a total of  $\leq 6$  episodes or  $> 6$  episodes over the 2-day diary collection period]) as factor. A hierarchical analysis strategy to adjust for multiplicity will not be implemented.

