### 5.4.2 Number of Daytime Urgency Episodes

For each treatment cycle, the mean raw value, mean change from study baseline and 95% CI for the mean change from study baseline in daytime urgency episodes (arithmetic mean) over the 2-day diary period will be summarized by treatment group at post-treatment visits.

For BOTOX treatment cycle 1, the same ANCOVA model described in Section 5.4.1 will be used.

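### Should the primary ANCOVA include the randomisation stratum, as the responder and secondary tests do?

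*SAP*

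**What the plan says.** SAP 1.1 states that "patients will be stratified by baseline daytime urinary urgency incontinence episodes", with the cut between 6 and 7 episodes over the two diary days.

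For the primary variable (change in normalised daytime incontinence at week 12 of cycle 1), SAP 5.2.1 says the pairwise comparisons "will be evaluated using an ANCOVA model with study baseline value as covariate, and treatment group as factor". Protocol 7.3.1 agrees: "The hypotheses will be tested using an ANCOVA model with baseline value as covariate and treatment group as a factor". SAP 5.2.1 extends a similar analysis to the other timepoints, so the continuous primary variable is modelled without the stratum throughout.

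The remaining between-group tests do use the stratum:

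- **Responders on the primary variable (SAP 5.3.1):** the Cochran-Mantel-Haenszel (CMH) "method controlling for baseline daytime urinary urgency incontinence episodes". SAP 5.4.6 does the same for the modified TBS.
- **Micturitions (SAP 5.4.1):** an "ANCOVA model with study baseline value as covariate, and treatment group and stratification" as factors.
- **Urgency, volume voided and PinQ (SAP 5.4.2, 5.4.3, 5.4.5):** "the same ANCOVA model described in Section 5.4.1 will be used".

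Protocol 7.3.2.2 marks the contrast openly. The secondary variables follow the primary analysis "except that baseline daytime urinary urgency incontinence episodes" enter as a further factor. Where a stratum is used, SAP 2.1.1 specifies that "the actual strata will be used instead of the strata assigned by" site entry. Night-time incontinence (SAP 5.4.4) and duration of effect (SAP 5.5.1) have no between-group test.

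**The concern.** A factor used to stratify randomisation is normally carried into the analysis. If it predicts outcome and is left out, the standard error is too large for the balance that was achieved: the test is conservative and power is lost. Here it is left out of the one comparison under hierarchical type I error control and kept in the lesser ones, including a responder test built on the same diary counts. Neither document gives a reason. If the stratum carried substantial information, the main test would be needlessly imprecise in a trial whose sample size was justified by precision alone.

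**Working it through.** **1. Are the models alike apart from the stratum?**

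| Test | Continuous covariate | Source of adjustment for baseline incontinence |
|---|---|---|
| Primary ANCOVA | Baseline daytime incontinence | The covariate itself |
| Micturitions, urgency, volume, PinQ ANCOVA | Baseline of that other variable | The stratum |
| Responder and TBS CMH | None stated | The stratum |

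Every planned test adjusts for baseline incontinence in some form. Only in the primary model would the stratum largely repeat a term already present.

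**2. The plan's precision figure (SAP 1.3).** Half-width = 1.96 x SD x sqrt(2/32) = 0.49 x SD. SD 2.0, 2.5, 3.0, 3.5 and 4.0 give 0.980, 1.225, 1.470, 1.715 and 1.960, as printed. Total N: 32/0.9 = 35.6, rounded up to 36; 3 x 36 = 108.

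**3. What adding the stratum would do.** The documents give neither the share of patients above 6 episodes nor the stratum's prognostic value, so these inputs are assumed:

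- over-dispersed 2-day urgency counts of at least 2, with 27% of patients above 6
- correlation between stratum and baseline covariate 0.79
- slope on baseline -0.5
- residual SD 3.0, inside the plan's range of 2.0 to 4.0
- stratum effect beyond linear baseline (g) of 0, 1 or 2 episodes/day

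Simulated ratio of 95% CI half-width, with stratum to without (lost degree of freedom included):

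| Per arm | g = 0 | g = 1 | g = 2 |
|---|---|---|---|
| 32 | 1.004 | 0.999 | 0.987 |
| 18 | 1.007 | 1.003 | 0.990 |
| 12 | 1.012 | 1.007 | 0.997 |

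In episodes/day at 32 per arm, the half-width goes from 1.490 to 1.496, 1.495 to 1.493, and 1.513 to 1.494. These values are t-based on a residual SD. The plan's 1.470 is normal-based on the SD of change, so the two are comparable in scale only.

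**4. Hand check at 32 per arm.** Leaving the stratum out raises the residual variance by about g² x p(1-p) x (1-r²) = g² x 0.27 x 0.73 x (1 - 0.79²) = 0.0741 g². Including it when it is uninformative multiplies the standard error by a simulated 1.0037.

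- g = 1: sqrt(9.0741/9) = 1.0041; 1.0037/1.0041 = 0.9996 (simulated standard error ratio 0.9991).
- g = 2: sqrt(9.2964/9) = 1.0163; 1.0037/1.0163 = 0.9876 (simulated 0.9871).

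**5. Break-even effect, below which adding the stratum costs precision.** At 32 per arm: g² = (1.0037² - 1) x 9/0.0741 = 0.90, so g = 0.95 (simulated 0.89). At 12 per arm the cost factor is 1.0105: g² = (1.0105² - 1) x 9/0.0741 = 2.56, so g = 1.60 (simulated 1.54). At 18 per arm the simulated value is 1.25. With the combined adult SD of 3.46 the simulated break-evens at 32, 18 and 12 per arm are 1.03, 1.44 and 1.79.

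For scale, Protocol section 1 gives adult reductions of 2.5 to 3.0 episodes/day on drug against about 1 on placebo, a difference of 1.5 to 2.0. A stratum effect of 2, over and above what baseline already explains, would match the top of that range.

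**6. Validity.** Across 12 to 32 per arm, simulated type I error was 0.041 to 0.057 without the stratum and 0.045 to 0.057 with it (simulation error 0.003). Mean bias stayed within 0.03 under both models.

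**7. Other assumptions.** A simulation with correlation about 0.75 and a true difference of 2.2 gave these results at 32 per arm:

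| g | Power without, % | Power with, % | Mean absolute shift in estimate |
|---|---|---|---|
| 0 | 81.9 | 81.6 | 0.038 |
| 1 | 82.4 | 83.0 | 0.059 |
| 2 | 81.0 | 82.4 | 0.101 |
| 3 | 78.2 | 81.6 | 0.152 |

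**The case for a change.** The best case for adding the stratum has four parts.

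- The covariate does not fully replace it. The stratum is a raw count of urgency incontinence, whereas the covariate is a 12-hour-normalised daily average of all daytime incontinence. The assumed correlation of 0.75 to 0.79 is below 1.
- The primary comparison is the only one under the fixed-sequence procedure, so an unexplained departure is most visible there.
- The actual stratum is already derived for other analyses, so adding it needs no new data.
- If the stratum predicted very strongly, the gain would be real: at 3 episodes/day beyond baseline, the half-width at 32 per arm falls from 1.57 to 1.49, about 5%.

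The facts stand, and so does the absence of a stated reason. They do not amount to a fault. The size of the non-redundant part is what the calculation measures, and it is small over the range up to 2 episodes/day. The 5% gain needs an effect larger than the whole adult drug-placebo difference. The primary comparison is also not the only one tested: SAP 2.3 applies the 0.05 level to all statistical tests, and Protocol 7.3 does so for efficacy without multiplicity adjustment unless specified otherwise. Cheap data do not make the change an improvement, because it would alter a prespecified primary model on which both documents agree. SAP 15 records that recruitment was stopped. If 12 per arm remained, the upper stratum would hold about 0.27 x 12 = 3 patients per arm.

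SAP 5.2.2 does not list the fixed effects of the MMRM, so whether that model carries the stratum is unknown. That does not bear on the validity of the primary ANCOVA.

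**Conclusion.** The concern does not hold. The primary model is prespecified identically in protocol and SAP, it is valid, and it adjusts for baseline severity through a finer measure than the stratum. The apparent inconsistency disappears once the covariates are compared, although this rationale is inferred from the structure and not written down. A sentence giving the reason would help a reader but would change no result.

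For stratum effects of 0 to 2 episodes/day, adding the factor moves the half-width by +0.4% to -1.3% at 32 per arm, +0.7% to -1.0% at 18 and +1.2% to -0.3% at 12. These sizes rest on assumed inputs: the share in the upper stratum, the covariate-stratum correlation, a residual SD of 3.0 and the stratum's effect. Final N is not given, so the arm sizes below 32 are illustrations. Including or leaving out a nearly redundant two-level factor is a choice on which competent statisticians may differ.

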### 5.2.2 Other Analyses of Primary Efficacy Variables

As a sensitivity analysis of the LOCF imputation method, mixed-effect model repeated measures analysis (MMRM) ([Mallinckrodt et al, 2001a](#) and [2001b](#)) will be conducted on the

primary efficacy variable with the observed data. The data will include all the observed cases up to and including the primary timepoint (week 12 after the first treatment). The unstructured variance-covariance structure will be used in the model. In contrast to LOCF that imputes missing values by carrying the last observed values forward, sensitivity analysis using MMRM allows for estimation of patient's missing response by using all the observed data and nonconstant correlations among the timepoints.

### **5.3 Secondary Efficacy Analyses**

#### **5.3.1 Proportion of Responders**

Responder analyses will be performed using the daily average frequency of normalized daytime urinary incontinence episodes. The following definitions of responder will be used for daytime urinary incontinence at week 12 post-treatment 1.

1. A responder is a patient who has at least a 50% reduction from study baseline in daily average frequency of normalized daytime urinary incontinence episodes at week 12 post-treatment 1.
2. In addition, the proportions of patients with 100% reduction from study baseline in daily average frequency of normalized daytime urinary incontinence episodes at week 12 post-treatment 1 will be evaluated.

For week 12 posttreatment 1, the difference of the proportions of patients responding between the treatment groups (100 versus 25 U of BOTOX, and 50 versus 25 U of BOTOX) will be analyzed using the Cochran-Mantel-Haenszel (CMH) method controlling for baseline daytime urinary urgency incontinence episodes (a total of  $\leq 6$  episodes or  $> 6$  episodes over the 2-day diary collection period).

For each treatment cycle, the proportion of patients with  $\geq 50\%$ , and 100% reduction from study baseline in normalized daytime urinary incontinence episodes will be presented by treatment group for each post-treatment visit.

### **5.4 Efficacy Analyses for the Secondary Efficacy Variables**

No imputation will be done for the missing values of the secondary efficacy variables. Efficacy analyses for the secondary efficacy variables will also be conducted with normalization to a 12-hour daytime period unless specified otherwise. The hierarchical analysis strategy to adjust for multiplicity will not be implemented.

### 5.4.1 Number of Daytime Micturition Episodes

For each treatment cycle, the mean raw value, mean change from study baseline, and 95% CI for the mean change from study baseline in daily average frequency of daytime micturition episodes (arithmetic mean) over the 2-day diary period will be summarized by treatment group at post-treatment visits.

For BOTOX treatment cycle 1, the treatment difference (LS mean difference) and 95% CI of the treatment difference in mean change from study baseline for 100 versus 25 U of BOTOX and 50 versus 25 U of BOTOX will be calculated. Pairwise comparisons of 100 versus 25 U of BOTOX and 50 versus 25 U of BOTOX up to week 12 posttreatment 1 will be evaluated using an ANCOVA model with study baseline value as covariate, and treatment group and stratification (baseline daytime urinary urgency incontinence episodes [a total of  $\leq 6$  episodes or  $> 6$  episodes over the 2-day diary collection period]) as factor. A hierarchical analysis strategy to adjust for multiplicity will not be implemented.

### 5.4.2 Number of Daytime Urgency Episodes

For each treatment cycle, the mean raw value, mean change from study baseline and 95% CI for the mean change from study baseline in daytime urgency episodes (arithmetic mean) over the 2-day diary period will be summarized by treatment group at post-treatment visits.

For BOTOX treatment cycle 1, the same ANCOVA model described in Section 5.4.1 will be used.

### 5.4.3 Volume (mL) per Micturition

Volume per micturition will be derived from the total volume voided over 1 daytime period during the 2-day bladder diary collection period divided by the number of voids in the same daytime period.

For each treatment cycle, the mean raw value, mean change from study baseline, and 95% CI for the mean change from study baseline in volume per micturition (arithmetic mean) over the 2-day diary period will be summarized by treatment group at post-treatment visits.

For BOTOX treatment cycle 1, the same ANCOVA model described in Section 5.4.1 will be used.

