6.3.8 Volume Voided Per Micturition

Average volume voided per micturition will be determined from the total volume voided measured over one daytime (waking hours) period during the 2-day bladder diary period, divided by the number of individual entries of volume voided in the same daytime period.

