12.3 Total Volume Voided Collection

Supplies:

- bladder diary
- urine collection containers

Schedule:

Collected over one daytime period (waking hours) during the 2-day bladder diary collection during screening and prior to each posttreatment visit.

Preparation:

All patients will use a bladder diary to record their daytime total volume voided data. Patients will measure their urine each time they void during the day (voluntary and catheterization as appropriate). Prior to receiving their bladder diary, patients will be trained by the site on the use of the diary and the data to be collected.

The site will provide the patient with the required urine collection containers. This container should be used to measure each void during the daytime period.

On the day that the patient selects to collect their daytime volume voided, they should adhere to the recommended daily fluid intake indicated to them by the investigator at the time they enter the study.

The patient will be instructed to clean the urine collection container after each void. This is to avoid contamination. In addition, the patient should understand that in order to record accurate data they must ensure that the urine collection container is empty and dry prior to each use.

The patient will be instructed to measure the volume of each void as it occurs and enter the amount into their diary. The patient will be instructed to place the urine collection container on a flat surface prior to recording the urine volume to ensure the measurement is recorded accurately. The patient should record the time and the amount of urine voided as soon as possible after each void.

The patient will be instructed to begin collecting urine with the first urination of the day (first morning void) and to collect and measure urine up to and including their last void before going to bed.

The site must instruct the patient NOT to estimate the measurements if the urine collection container is not used, although the patient should record all other diary information required for the void. The patient should resume measuring at the next void.

If patient's visit day is rescheduled, the study coordinator must ensure adequate time has been provided for the patient to record 2 diary data days including 1 daytime total volume voided collection in the week prior to the rescheduled visit.

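### SAP 5.4.3 divides measured volume by all voids, not by measured voids, so volume per micturition is too low whenever a void is recorded without a volume

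*SAP*

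**What the plan says.** Volume voided per micturition is a secondary efficacy variable (protocol 7.2.2). The two documents define it differently.

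- **Protocol 6.3.8:** total volume from one daytime period, "divided by the number of individual entries of volume voided in the same daytime period".
- **SAP 5.4.3:** the volume total of a single day of the diary, "divided by the number of voids in the same daytime period".

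Protocol Attachment 12.3 says what to do when a void is not measured. Sites are to tell patients "NOT to estimate the measurements if the urine collection container is not used". The void itself still goes into the diary: "although the patient should record all other diary information required for the void". Measuring then continues on the same day: "The patient should resume measuring at the next void".

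SAP 5.4 adds: "No imputation will be done for the missing values of the secondary efficacy variables". It also applies 12-hour normalisation to the secondary variables unless an exception is stated, and 5.4.3 states none. SAP section 13 declares no deviations from the protocol, and the amendment table in section 15 lists no change to 5.4.3.

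**The concern.** A void recorded without a volume is missing from the numerator but present in the SAP denominator, so in effect it is counted as a void of 0 mL. The protocol's denominator leaves it out of both. Attachment 12.3 makes partly measured days an instructed outcome, because the patient skips the measurement, records the void and goes on measuring. Each assessment rests on one daytime period, so a missed measurement is not averaged over further days.

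The variable is compared between doses by ANCOVA, with the baseline value as covariate. Under the SAP rule, part of what is analysed is how completely each diary was measured. A patient who measures more carefully at week 12 than at screening appears to void larger volumes. A programmer following the SAP would produce a different endpoint from the protocol's, and nothing in the SAP tells the reader so.

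**Working it through.** **Inputs.** The two denominators and the recording rule are quoted above. Eight voids per day is the minimum average at entry (protocol 4.3, criterion 6); 10 and 12 are illustrative. Volumes of 150 mL at baseline and 180 mL at week 12 are assumptions, since the documents give none. The percentages do not depend on them. The plan states no figure for this endpoint, so there is nothing to reproduce.

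**1. Relation between the two rules.** Let n be the recorded voids, m the measured voids and V the sum of the measured volumes.

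- Protocol value = V/m
- SAP value = V/n = (m/n) × (V/m)
- Relative difference = −(n − m)/n, the unmeasured share

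**2. Size within one day.**

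| Recorded voids | 1 unmeasured | 2 unmeasured | 3 unmeasured |
|---|---|---|---|
| 8 | −12.5% | −25% | −37.5% |
| 10 | −10% | −20% | −30% |
| 12 | −8.3% | −16.7% | −25% |

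With 8 voids of 150 mL, the protocol rule returns 150 mL in every column. The SAP rule returns 131.25, 112.5 and 93.75 mL.

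**3. Against the true mean per void.** The percentages are exact against the protocol value. They are exact against the truth only if unmeasured voids have the same mean volume as measured ones. The direction needs no such assumption: leaving a positive volume out of the sum while keeping n always gives too low a value. In 10,000 simulated days (8 voids drawn uniformly from 50 to 300 mL, one unmeasured), the SAP value was below the true mean on all 10,000. The protocol value was below it on 5,061 and above it on 4,939.

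**4. Change from baseline in one patient** (8 voids, 150 to 180 mL, true change +30 mL).

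- One unmeasured at week 12 only: 180 × 7/8 − 150 = +7.5 mL
- One unmeasured at baseline only: 180 − 150 × 7/8 = +48.75 mL
- One unmeasured at both: 157.5 − 131.25 = +26.25 mL

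With no true change, 10 voids of 150 mL and two unmeasured at baseline only, the SAP rule reads 150 × 8/10 = 120 mL, then 150 mL. That is a false gain of 30 mL, or 30/120 = 25%.

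**5. Group mean.** Fully measured diaries dilute these figures. Suppose a fraction f of diaries has one of 8 voids unmeasured and the rest are complete. The mean is then low by f × 12.5%. For assumed f of 10%, 50% and 100% and a mean of 180 mL, this is 2.25, 11.25 and 22.5 mL. A false difference between doses at week 12 comes from the difference in this quantity between arms.

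**6. No volume measured.** With m = 0 the protocol ratio is undefined. The SAP formula could return 0 mL, since V = 0 and n > 0, unless the day is set to missing. No rule covers this.

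**7. Normalisation.** Volume per void is not a rate over time. If the 12-hour factor were applied to the ratio, a 16-hour day (one of the SAP's own examples in 2.3.1) would multiply it by 12/16 = 0.75 and turn 150 mL into 112.5 mL.

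**The case against.** The strongest reply is that the SAP wording is a loose paraphrase. Its denominator could mean the voids that make up the measured total. SAP 2.3.1 describes the diary as collecting a volume for each void on that day, and protocol 6.3.7 asks patients to measure every void; if they do, the two counts are the same. The declaration of no deviations fits that reading. It is possible, but the SAP nowhere limits the count to voids with a volume, and the protocol wording that did so was not carried over. Attachment 12.3 expressly provides for voids without one.

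The other objections limit the size, and they stand:

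- The frequency of unmeasured voids is unknown. Training, supplied containers and the duty to notify the sponsor of an uncompleted collection should keep it down.
- The 25% false gain is a single-patient illustration with unfavourable asymmetry, not a group estimate.
- Allocation is randomised, and patients and investigators are blinded to dose. A shift in completeness common to all arms largely cancels between doses, and an equal unmeasured share only shrinks differences. A false dose difference needs unmeasured shares that differ by arm. That could happen with equal numbers of missed voids if one dose lowers voiding frequency more (one missed void is 12.5% of 8 but 8.3% of 12), but the documents give no evidence on it.
- The variable is secondary and outside the hierarchical testing.

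**Conclusion.** The concern holds. As written, the SAP rule departs from protocol 6.3.8 and understates volume per micturition on every partly measured day. The understatement equals the unmeasured share: 12.5% for one void in eight, 20% for two in ten. That size is exact relative to the protocol's value, and the downward direction is certain.

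The effect on the trial's results cannot be stated, because the documents do not report how many voids go unmeasured. Within-group changes are exposed whenever completeness shifts between screening and follow-up; dose contrasts are exposed mainly when it differs by arm. Where every void is measured, the two rules agree. The correction should be made because the error has a fixed direction, affects a variable compared between doses, and is not declared.

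**What to change.** In SAP 5.4.3:

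1. Define the denominator as the number of voids with a recorded volume in that daytime period, as protocol 6.3.8 does.
2. Set the value to missing if the day has no volume entry.
3. State that this ratio is not normalised to 12 hours, as an explicit exception to SAP 5.4.

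If the sponsor does intend to divide by all voids, that choice should be listed and justified in SAP section 13.

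The cost is a few words in the SAP and about one line of derivation code. No new data are needed, because the volume entries are already in the diary. A count of recorded voids without a volume, by dose group and visit, would show whether the choice matters in this trial.
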